#### **12.4.2 Analysis of Secondary Endpoints**

Secondary endpoints of the objective response proportion and 12-month overall survival (OS) will be calculated and 95% confidence intervals will be estimated via binomial proportions.

OS will also be estimated using the Kaplan-Meier method, and 95% confidence intervals for OS estimates (including median OS) will be calculated using Greenwood's formula.

Pattern of disease progression will focus on the rates of progression in the radiated lesions vs non-radiated lesions and rates of new lesions.

### **12.5 Interim Analysis**

No interim analysis for efficacy is planned. Interim analyses for safety will be performed as outlined in Section 12.1.

### **12.6 Reporting and Exclusions**

#### **12.6.1 Evaluation of Toxicity**

All subjects will be evaluable for toxicity from the time of their first treatment with carboplatin or cisplatin with etoposide and durvalumab or their first radiation fraction.

#### Hy's Law

Cases where a patient shows elevations in liver biochemistry may require further evaluation and occurrences of AST or ALT  $\geq 3 \times$  ULN together with total bilirubin  $\geq 2 \times$  ULN may need to be reported as SAEs. Please refer to Appendix B, the Toxicity Management Guidelines, for further instruction on cases of increases in liver biochemistry and evaluation of Hy's law.

### 12.6.2 Evaluation of Response

All subjects included in the study will be assessed for response to treatment if they have received at least 1 cycle of platinum plus etoposide chemotherapy with durvalumab and completed radiation.

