### **6. Study Procedures**

#### **6.1 Schedule of Assessments**

**Table 1. Schedule of trial events**

	Screening D -28 to D-1	Cycle 1					Cycles 2 - 4			C5D1+ (D85+)	EOT
		D1	D2	D3	D4	D5	D1	D2	D3		
Carboplatin/Cisplatin		X					X				
Etoposide		X	X	X			X	X	X		
Durvalumab		X					X			X a	
Radiation b		X	X	X	X	X					
Informed consent	X										
Inclusion/Exclusion criteria review	X										
Radiation Simulation	X										
Medical history	X	X					X			X a	X
Physical exam	X	X					X			X a	X
Concurrent Medications	X	X					X			X a	X
Vital signs including Height and Weight	X	X					X			X a	X
CT or PET-CT c	X						X d			X d,e	
MRI Brain f	X						X d,g			X d,e,g	
CBC w/diff	X	X					X			X a	X
Serum chemistry with LFTs	X	X					X			X a	X
Amylase and/or Lipase	X	X					X			X a	X
Thyroid Function Panel	X	X					X			X a	X
Hepatitis A, B, C Profile	X										
Beta-hCG h	X	X					X			X	X
Adverse event Capture	Continuous Assessment										
Blood for correlative studies		X					X			X i	X
Research biopsy (Optional)	X									X i	X

a After D85, repeat every 28 days (+/- 7 days) until disease progression

b Exact radiation schedule to be determined by treating Radiation Oncologist; all five fractions of radiation should be completed within 2 weeks of first radiation dose (>3 weeks is an acceptable variation); SBRT is preferred but 3D-CRT and IMRT are permitted.

c CT scans of the Chest and Abdomen/Pelvis with or without Contrast; PET-CT Skull Base to Thigh

d Imaging can be done +/- 7 days

e After D85, repeat every 8 weeks +/- 7 days until disease progression

f MRI Brain with and without Contrast

g MRI Brain only needs to be done at this time point if subject was found to have brain metastases at baseline assessment; otherwise MRI Brain can be done as clinically indicated

h For pre-menopausal females of childbearing potential

i After D85, repeat every 8 weeks (+/- 7 days) until D365

j Optional Research Biopsy can be done +/- 21 days

Abbreviations: C = Cycle; D = Day; diff = differential; LFTs = Liver Function Tests; EOT = End of Treatment

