## **8. Study Intervention Discontinuation and Participant Discontinuation/Withdrawal**

### **8.1 Discontinuation of Study Intervention**

An individual subject who is discontinued from the study will not receive any further investigational product. An investigator may discontinue a participant from the study for the following reasons:

1. If any clinical adverse event (AE), laboratory abnormality, or other medical condition or situation occurs such that continued participation in the study would not be in the best interest of the participant
2. Disease progression which requires discontinuation of the study intervention
3. If the participant meets an exclusion criterion (either newly developed or not previously recognized) that precludes further study participation because continuing investigational therapy might constitute a safety risk
4. Participant unable to receive radiation, chemotherapy, or ICB therapy for 12 weeks.
5. Withdrawal of consent or *participant lost to follow-up after several attempts to contact subject to schedule study visit.*
6. Adverse event related to radiation or chemotherapy that, in the opinion of the investigator or the sponsor, contraindicates further treatment with these modalities
7. Pregnancy or intent to become pregnant

8. Adverse event related to durvalumab that is Grade  $\geq 3$ , with the exception of toxicities that do not meet criteria for discontinuation as per guidelines in Appendix B or per NCCN Clinical Practice Guidelines in Oncology Management of Immunotherapy-Related Toxicities.
9. Grade  $\geq 3$  infusion reaction
10. Subject noncompliance that, in the opinion of the investigator or sponsor, warrants discontinuation, such as refusal to adhere to scheduled visits or initiation of alternative anticancer therapy including another investigational agent

Discontinuation from study intervention does not mean discontinuation from the study, and remaining study procedures should be completed as indicated by the study protocol. If a clinically significant finding is identified (including, but not limited to, changes from baseline) after enrollment, the investigator or qualified designee will determine if any change in participant management is needed. Any new clinically relevant finding will be reported as an adverse event (AE).

The data to be collected at the time of study intervention discontinuation will include the following:

- Interval Medical History
- Concurrent Medications

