## **8.2 Participant Discontinuation/Withdrawal from the Study**

Participants are free to withdraw from participation in the study at any time upon request.

The reason for participant discontinuation or withdrawal from the study will be recorded on the Case Report Form (CRF). Subjects who sign the informed consent form but do not receive the study intervention may be replaced. Subjects who sign the informed consent form and receive the study intervention, and subsequently withdraw, or are withdrawn or discontinued from the study, will not be replaced.

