## **10.3 Response Criteria**

Response will be assessed based on imaging as per RECIST 1.1 criteria. The Overall Response Rate (ORR) will be calculated by the proportion of subjects achieving a RECISTv1.1 complete or partial response.

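### Section 12.6.2 limits response assessment to subjects who completed radiation, which on its natural reading drops treated early failures from the response rate

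*Combined protocol and SAP*

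**What the plan says.** Section 12.6, Reporting and Exclusions, holds two rules on who is evaluated.

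- **Toxicity (12.6.1):** "All subjects will be evaluable for toxicity from the time of their first treatment", where first treatment means the first systemic treatment or the first radiation fraction.
- **Response (12.6.2):** subjects are assessed "if they have received at least 1 cycle of platinum plus etoposide chemotherapy with durvalumab and completed radiation".

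The response rate itself appears in two places. Section 10.3 says it is "calculated by the proportion of subjects achieving a RECISTv1.1 complete or partial response". Section 12.4.2 says "Secondary endpoints of the objective response proportion and 12-month overall survival (OS) will be calculated", with 95% binomial confidence intervals and no test. Neither names a denominator or says how a subject without an assessment is counted.

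For the primary 12-month PFS endpoint, Sections 1, 3.1, 4.5 and 12.2 plan 42 enrolments to yield 34 evaluable subjects, and Sections 12.1 and 14.1 continue accrual until 34 are evaluable. No section defines that term for PFS. Section 8.2 says of consented subjects who go untreated: "Subjects who sign the informed consent form but do not receive the study intervention may be replaced". Of treated subjects, it says that those who "subsequently withdraw, or are withdrawn or discontinued from the study, will not be replaced".

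**The concern.** Completing radiation is an outcome of the early treatment course, not a baseline characteristic. Subjects who fail the condition do so because of early death, toxicity, clinical decline or withdrawal, and such subjects can be expected to respond less often. A rate computed without them describes those who got through radiation, not those who were given the regimen.

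The trial has one arm, and Section 3.2 reads its results against the durvalumab arm of CASPIAN. A response rate from a selected subset is harder to set beside a historical figure. The condition also sits awkwardly with Section 8.1, which says "Discontinuation from study intervention does not mean discontinuation from the study" and keeps the remaining study procedures going.

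**Working it through.** **1. Can a treated subject fail the condition before the first scan?** Section 6.1.2.1 lets radiation start as late as Cycle 2 Day 3. Cycle 2 Day 1 is nominal Day 22, so this is Day 24. Sections 7.3.15.1 and 7.5 allow 2 to 3 weeks for the five fractions: 24 + 14 = Day 38, 24 + 21 = Day 45. The first on-treatment scan is due about Day 43 (Section 6.1.2.3). With a late start, completion can therefore fall as late as the first scan. With the preferred Day 1 start and Table 1's "all five fractions of radiation should be completed within 2 weeks of first radiation dose", the exposure is much shorter. Few exclusions are likely, but not none: Section 4.2 admits some subjects with ECOG PS 2 and requires only 12 weeks' life expectancy.

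**2. Effect on the response rate.** Let N subjects be treated and k be left out, with N − k = 34. Let p be the true rate in all treated subjects and q the rate in those left out. Then

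apparent rate = (pN − kq) / 34.

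The documents give no response rate and no k. Assume p = 60% for illustration.

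| k left out | N | q = 0 | q = 30% | q = 60% |
|---|---|---|---|---|
| 2 | 36 | 21.6/34 = 63.5% | (21.6 − 0.6)/34 = 61.8% | 60% |
| 4 | 38 | 22.8/34 = 67.1% | (22.8 − 1.2)/34 = 63.5% | 60% |

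If all 8 subjects between 42 and 34 were treated, left out and non-responders, the rate would read 25.2/34 = 74.1%. That is an outer limit, not a forecast. For scale, the 95% half-width at 60% with 34 subjects is 1.96 × √(0.60 × 0.40/34) = 16.5 points. The shift is smaller than sampling error in the cases tabulated, but if q is below p it always goes upward and the interval does not reflect it.

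**3. The primary-endpoint figure, for reference.** Section 12.1 gives 18% versus 38%, two-sided 0.05, 80% power and 34 subjects.

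n = [(1.96 × √(0.18 × 0.82) + 0.842 × √(0.38 × 0.62)) / 0.20]² = 33.7, so 34.

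The plan's number reproduces. The chi-square test rejects upward at 11 or more of 34, with exact power 80.2% at 38%.

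**4. Why the population behind the 38% needs stating.** The 80.2% holds for 34 treated subjects if 38% describes all of them. Suppose instead that it describes radiation completers, and that 2 or 4 of the 34 do not complete and all fail. The all-treated rate is then 0.38 × 32/34 = 35.8% or 0.38 × 30/34 = 33.5%, and power is about 72% or 62%.

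**The case against.** Section 12.6.2 says who is assessed; it does not state a denominator, and Section 10.3 speaks simply of subjects. Scans are scheduled whether or not radiation was finished, so an all-treated rate is not ruled out. The endpoint is secondary and untested, both the 60% and the counts are assumptions, and the documents give no historical response rate from which to measure harm. All of this stands, and it limits the size of the point. It does not remove it: the sentence sits under a heading on exclusions, beside a toxicity rule written to take in every treated subject, and nothing elsewhere puts the others back as non-responders.

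A reader might go further and infer that the same condition governs the 12-month PFS test and inflates its false-positive rate. The documents do not support that. Section 12.6.2 does not mention PFS, Section 10.1 counts from the start of study treatment, Section 12.6.1 takes all treated subjects for the other primary endpoint, and Section 8.2 does not replace treated subjects. Nor does any section say that the 8 extra enrolments are treated failures to be left out, or that they cover untreated subjects; the allowance is simply unexplained.

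**Conclusion.** The point holds for the response rate and should be fixed. As written, Section 12.6.2 conditions on a post-treatment outcome and can overstate the rate. On the illustrative 60%, the overstatement is about 2 to 7 points for 2 to 4 subjects left out, and zero if they respond as often as the rest. This rests on the natural reading of the sentence and on assumed rates and counts.

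For 12-month PFS there is a missing definition, not a demonstrated bias. The lean towards all treated subjects is clear, but three things leave it open: the unexplained allowance, the description in Section 12.1 of the 34 as patients receiving radiation as well, and an accrual rule that would conflict with Section 8.2 if treated subjects could be classed as not evaluable. Defining the term would not settle everything. Section 12.4.1 uses a binomial proportion, and no rule says how a subject lost before 12 months is counted.

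**What to change.** **Response rate.** In Section 12.6.2, make every subject who receives any protocol treatment, on the terms of Section 12.6.1, the primary response set, and count those without a response assessment as non-responders. Keep the completed-radiation set as a secondary analysis. Before it can be used, the completion window must be reconciled: the Table 1 footnote calls more than 3 weeks an acceptable variation, while Sections 7.3.15.1 and 7.5 call it unacceptable. This change is wording only and needs no new data. The price is that the reported rate may be lower.

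**Clarification for 12-month PFS.** Define which subjects are evaluable, state which population the 38% describes, say what the allowance from 42 to 34 covers, and say how unknown 12-month status is counted. This is partly a design decision. Stopping at 34 treated gives 80.2% power only if 38% applies to all treated subjects and every status is known. If all 42 were treated and analysed, the test would reject at 13 or more and power would be 86.5%.

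**Separate matter.** Section 10.1 first counts death without qualification as a PFS event, then treats death as progression only if it is due to the malignancy. Those two sentences must be reconciled whatever analysis set is chosen.

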## 13. Adverse Event Reporting Requirements

### 13.1 Reporting

Adverse event (AE) monitoring and reporting is a routine part of every clinical trial. The investigator will be required to provide appropriate information concerning any findings that suggest significant hazards, contraindications, side effects, or precautions pertinent to the safe use of the drug or device under investigation. Safety will be monitored by evaluation of adverse events reported by subjects or observed by investigators or research staff, as well as by other investigations such as clinical laboratory tests, x-rays, electrocardiographs, etc.

#### 13.1.1 Reporting of Deaths to AstraZeneca

All deaths must be recorded and reported as outlined in Section 13.2.2 and 13.4.3. In addition, all SAEs resulting in death or death of unknown cause must be reported to AstraZeneca via [contact] within 7 calendar days of awareness or sooner when required

#### 13.1.2 Overdose

An overdose is defined as a patient receiving a dose of durvalumab in excess of that specified in the Investigator's Brochure, unless otherwise specified in this protocol. Any overdose of a study patient with durvalumab, with or without associated AEs/SAEs, is required to be reported within 24 hours of knowledge of the event to the sponsor. The sponsor must report these to AstraZeneca/MedImmune Patient Safety or designee using the designated Safety e-mailbox (see Section 13.4.3 for contact information) within 7 calendar days or sooner when required. If the overdose results in an AE, the AE must also be recorded as an AE. Overdose does not automatically make an AE serious, but if the consequences of the overdose are serious, for example death or hospitalization, the event is serious and must be recorded and reported as an SAE (see Section 13.4.3). There is currently no specific treatment in the event of an overdose of durvalumab.

#### 13.1.3 Hepatic Function Abnormality

Hepatic function abnormality that fulfills the biochemical criteria of a potential Hy's Law

case in a study patient, with or without associated clinical manifestations, is required to be reported as “hepatic function abnormal” within 24 hours of knowledge of the event to the sponsor. The Sponsor must report these events to AstraZeneca Patient Safety using the designated Safety e-mailbox (see Section 13.4.3 for contact information) within 7 calendar days or sooner when required, unless a definitive underlying diagnosis for the abnormality (e.g., cholelithiasis or bile duct obstruction) that is unrelated to investigational product has been confirmed. The criteria for a potential Hy’s Law case is Aspartate Aminotransferase (AST) or Alanine Aminotransferase (ALT)  $\geq 3$  times Upper Limit of Normal (ULN) together with Total Bilirubin (TBL)  $\geq 2$  times ULN at any point during the study following the start of study medication irrespective of an increase in Alkaline Phosphatase (ALP).

- If the definitive underlying diagnosis for the abnormality has been established and is unrelated to investigational product, the decision to continue dosing of the study patient will be based on the clinical judgment of the investigator.
- If no definitive underlying diagnosis for the abnormality is established, dosing of the study patient must be interrupted immediately. Follow-up investigations and inquiries must be initiated by the investigational site without delay.

Each reported event of hepatic function abnormality will be followed by the investigator and evaluated by the sponsor and AstraZeneca/MedImmune.

### **13.1.4 Pregnancy**

#### Maternal exposure

If a patient becomes pregnant during the course of the study, the IPs should be discontinued immediately.

Pregnancy itself is not regarded as an AE unless there is a suspicion that the IP under study may have interfered with the effectiveness of a contraceptive medication.

Congenital abnormalities or birth defects and spontaneous miscarriages should be reported and handled as SAEs. Elective abortions without complications should not be handled as AEs. The outcome of all pregnancies (spontaneous miscarriage, elective termination, ectopic pregnancy, normal birth, or congenital abnormality) should be followed up and documented even if the patient was discontinued from the study.

If any pregnancy occurs in the course of the study, then the Investigator or other site personnel should inform the sponsor within 1 day, i.e., immediately, but no later than 24 hours of when he or she becomes aware of it.

The sponsor will work with the Investigator to ensure that all relevant information is provided within 1 to 5 calendar days. The Sponsor must report to AstraZeneca Patient Safety using the designated Safety e-mailbox (see Section 13.4.3 for contact information) within 7 calendar days or sooner when required for pregnancies with SAEs and within 30 days for all other pregnancies.

The same timelines apply when outcome information is available.

#### Paternal exposure

Male patients should refrain from fathering a child or donating sperm during the study and for 180 days after the last dose of durvalumab + any drug combination therapy or 90 days after the last dose of durvalumab monotherapy, whichever is the longer time period.

Pregnancy of the patient’s partner is not considered to be an AE. However, the outcome of all pregnancies (spontaneous miscarriage, elective termination, ectopic pregnancy,

normal birth, or congenital abnormality) occurring from the date of the first dose until 180 days after the last dose of durvalumab + any drug combination therapy or 90 days after the last dose of durvalumab monotherapy, whichever is the longer time period should, if possible, be followed up and documented.

Where a report of pregnancy is received, prior to obtaining information about the pregnancy, the Investigator must obtain the consent of the patient's partner. Therefore, the local study team should adopt the generic ICF template in line with local procedures and submit it to the relevant Ethics Committees (ECs)/Institutional Review Boards (IRBs) prior to use.

### **13.2 Adverse Event Definition**

An adverse event (also referred to as an adverse experience) can be any unfavorable and unintended sign (e.g., an abnormal laboratory finding), symptom, or disease temporally associated with the use of a drug and does not imply any judgment about causality. An adverse event can arise with any use of the drug (e.g., off-label use, use in combination with another drug) and with any route of administration, formulation, or dose, including an overdose.

#### **13.2.1 Disease Progression**

Disease progression can be considered as a worsening of a patient's condition attributable to the disease for which the IP is being studied. It may be an increase in the severity of the disease under study and/or increases in the symptoms of the disease. The development of new or progression of existing metastasis to the primary cancer under study should be considered as disease progression and not an AE. Events that are unequivocally due to disease progression should not be reported as an AE during the study.

#### **13.2.2 Deaths**

All deaths that occur during the study treatment period, or within the protocol-defined follow-up period after the administration of the last dose of study drug, must be reported as follows:

- Death clearly resulting from disease progression should be reported and documented in the CRF, in the Statement of Death page. It should not be reported as an SAE.
- Where death is not due (or not clearly due) to progression of the disease under study, the AE causing the death must be reported.
- The report should contain a comment regarding the co-involvement of disease progression, if appropriate, and should assign main and contributory causes of death.
- Deaths with an unknown cause should always be reported as an SAE. It should also be documented in the Statement of Death page in the CRF.

#### **13.2.3 Investigational Agent or Device Risks (Expected Adverse Events)**

As the combination of platinum + etoposide chemotherapy and Durvalumab immunotherapy is now FDA-approved for patients with ES-SCLC, the "investigational

agent" in this study will be the sub-ablative radiation. Mild to moderate (grade <3) adverse events from thoracic radiation include the following: esophagitis, dermatitis, radiation recall reaction, pleural effusion, pericardial effusion, pleuritic pain, non-cardiac chest pain, chest wall pain, pneumonitis, atelectasis, cough, dyspnea, pulmonary fibrosis, generalized muscle weakness, fatigue, photosensitivity, telangiectasias, FEV decrease, WBC decrease, lymphocyte count decrease, and neutrophil count decrease. Severe adverse events (grade ≥3) from radiation may also include the above mentioned plus those listed in Table 6.

